
Intervention
	
Infant Parent Support (a multidisciplinary infant mental health team aiming to improve the mental health of children aged 0-5 with a social worker).
 
Primary, Phase 1: Coproducton, with parents of children who have a social worker, of the IPS intervention.
 
Secondary, Phase 1: preliminary mapping of service context.
 
Primary, Phase 2: Recruitment and retention (at 3 and 6 months) to a feasibility RCT.

Outcomes
	
Secondary:
 
 >Improvement in the organisation, access, and quality of services, for children with a social worker and mental health issues. >Examination of putative primary and secondary outcomes for a future definitive RCT of IPS (see below) >Development of a parent-supported outcome measure and a parent-supported experience measure for use in a future definitive RCT >Whether it is possible to expand into new sites to conduct a successful Phase III trial.

Co-ordination
	
Local: by University of Glasgow trial office Central: by University of Glasgow trial office

Table of contents

“Partnership for Change”: Co-production and feasibility randomised controlled trial of an intervention to improve the mental health of children with a social worker	1
Summary	2
Table of contents	4
Background and Problem Statement.....	5
Background	5
Timeline.....	6
Aims	6
Methods	7
Rationale for the trial	7
Intervention and Theory of Change	13
Phase 1 – Intervention Coproduction.....	13
Phase 2 - Feasibility RCT	15
Theory of Change.....	16
Impact Evaluation	16
Research questions.....	16
Evidence of feasibility	16
Evidence of promise	17
Readiness for trial	17
Cost Evaluation	18
Outcomes	19
Methods.....	21
Sampling	21
Trial Recruitment	22
Screening for eligibility.....	24
Informed consent.....	24
Randomisation and allocation.....	24
Administration arrangements post recruitment.....	25
Data Collection.....	25
Baseline	25
Qualitative interviews.....	26
Video	27
Follow-up.....	27
End of Study.....	27
Analysis	28
Qualitative analysis.....	28
Quantitative Data analysis	30

Cost Evaluation (if appropriate)	30
Economic evaluation	30
Ethics	30
Ethics and regulatory approvals	30
Protocol compliance and amendment.....	31
Data Protection	32
Data recording and processing	34
Qualitative data management.....	34
Personnel.....	35
Qualifications and Experience of Applicants	35
Risk Management	42
Timeline	43
Outcome measures.....	45
References	45
Appendices	51

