For our feasibility RCT, we aim to recruit 30 families living in Glasgow or London, who are likely to benefit from IPS: families with problems severe enough that IPS will offer tangible benefits yet whose problems are not so entrenched that change is impossible, with an inclusive approach to social class, ethnicity, gender, sexuality, and disability. We wish to target families whose children are 'in need' (or the Scottish equivalent), do not yet have a child protection plan (are not yet on the child protection register), but are at risk of formal child protection proceedings. Just over three in every 100 English children are described as being 'in need', i.e., 'a child who is unlikely to reach or maintain a satisfactory level of health or development, or their health or development will be significantly impaired without the provision of children's social care services' and 13% of these children (~4 in every 1,000 English children) have a child protection plan (Gov, 2021). The signal for children likely to transition from "in need" to "child protection" is often a need for multi-agency support. Our preliminary plan for defining our target population is, therefore, children in need (or Scottish equivalent) who also have at least one additional service involved e.g., child and adolescent mental health services, paediatrics, or educational psychology and where a parent and/or child has a mental health problem or neurodevelopmental condition identified at initial trial screening. Further refining the definition of our target population will be a task of the qualitative process evaluation in Phase 1 of the research, and continued refinement might also be necessary during Phase 2.

Theory of Change

Impact Evaluation

Research questions

The pilot aims to address the following overarching research questions:

- Can we coproduce, with parent collaborators, a new service, Infant Parent Support (IPS), aiming to improve the mental health of children with a social worker?
- Can we test the feasibility of an RCT of IPS compared with services as usual?

Evidence of feasibility

- Can sufficient numbers of families be recruited and retained such that a full-scale RCT is likely to be feasible?
- Can the project expand to include new partners?
- What is the profile of services-as-usual (SAU) (including infant/adult mental health; social care statutory processes) at each site and can care pathways be improved?

Evidence of promise

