We intend to recruit a sample of 30 families in Phase 2, 15 families will be randomly allocated to each group. This number will be ideal for allowing us to investigate participant experiences and trial processes in detail. Since the purpose of the feasibility RCT is not to examine quantitative outcomes other than recruitment and retention rates, the information that we gather about the putative outcome measures for a definitive RCT, from this and other studies, will inform the sample size calculation for a future definitive RCT. Therefore, formal power calculations are not appropriate for this largely qualitative study. In our ongoing BeST² trial, that compares IFTs with services-as-usual, we have been successful in recruiting more than 50% of all families with children under age five coming into an episode of foster care, and we have not found any systematic biases in our recruitment compared to the base population. We have managed to retain 72% of these families over 2.5 years. This has been achieved through our partnership approach (Turner-Halliday et al., 2018): i. utilising the expertise of a senior social work manager co-investigator (in this current proposal - [name]), and ii. employing experienced social workers as Recruitment Coordinators (RCs). These RCs have limited access to local authority data systems (so can target the eligible population), are experienced in assessing capacity and ensuring families are fully informed before deciding whether or not to consent, and their seniority and networks encourage other social workers to engage in the research. We would use similar successful strategies in this proposed study.

[figure not shown]

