Once baseline data is collected, participants will be randomised. A central randomisation facility will randomise patients (1:1) to IPS or SAU. The randomisation list will be created by a computer program written by a statistician who will have no involvement with the final analysis. The randomisation list, the program that generated it and the random seed used will be stored in a secure network location.

Administration arrangements post recruitment

The University of Glasgow trial office, and researchers at Queen Mary University London, will be responsible for the following:

- Arranging an appointment with the participants at a mutually convenient time and place (e.g., community health centre/participant's home or online) to collect baseline data
- Providing the randomisation facility with participant details
- Informing the participant and any referring organisation of the outcome of randomisation
- Informing the appropriate contact person from IPS of the outcome of randomisation
- Contacting parents to remind them of follow -up assessment
- Arranging an appointment with the participant to collect follow-up data

Post randomisation, arrangements for support will then be taken forward by respective services, and the trial team will not be involved.

Data Collection

Baseline

Measuring outcomes (putative outcome measures for a future definitive RCT - expected sample size for each measure ~30). As these are putative measures for a future definitive RCT, none of these measures are included in the study to measure any of our outcomes but simply to see if they are appropriate and acceptable for a future definitive RCT. We will be looking at basic aspects of the data from these measures, such as missingness of data, mean scores and standard deviations (to support sample size calculations for a future definitive RCT), and - qualitatively - at whether parents perceive the questions asked to be measuring the right kinds of things and are happy with the burden and have any other comments about acceptability.

Target	Measure	Source
Child mental health	RADA, SDQ, PIRGAS and Quality of life measure (PEDs-QL)	• Parent self-report questionnaires •Health routine data
Child material circumstances	Service use data	• Routine data

		
 • Parent interviews – including demographics, benefits etc • Social worker interviews

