Through this iterative process, topics or areas of interest or debate not previously included in interview/focus group questions will be followed up on and explored further as the project progresses. This will allow for both pre-defined, and participant-led data to be gathered in a balanced way throughout the study.

Interview and focus group data will be transcribed verbatim and thematically analysed, according to the methodology of Braun and Clarke (Braun & Clarke, 2006), to identify themes including any recurrent and shared patterns of participant perceptions.

Qualitative work in phase 2 will follow MRC guidance (Moore et al., 2015) and aims to keep abreast of issues and themes uncovered in Phase 1, to explore drivers and barriers to safe/optimal IPS/SAU delivery at all trial sites. comprehensive information on the acceptability and feasibility of research procedures Data will be managed using NVivo qualitative data software and analysed thematically following Braun and Clarke's steps which include independent reading of transcripts to develop a coding frame, review and naming of codes, and development and reporting of key themes (Braun & Clarke, 2006). Findings will be fed back to PC and professional stakeholder groups (possibly using Delphi method or group feedback) in order to identify whether barriers and facilitators to services can be refined and developed into codesign responses.

Quantitative Data analysis

Quantitative analyses are not required: recruitment and retention rates will be simple percentages (Braun & Clarke, 2006).

Cost Evaluation (if appropriate)

Economic evaluation

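### The protocol says no quantitative analysis is required and fixes its primary outcomes as simple percentages, which contradicts its own planned descriptives and leaves the large uncertainty at 30 families unstated

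*Protocol*

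**What the plan says.** The Summary names the Phase 2 primary outcome: "Primary, Phase 2: Recruitment and retention (at 3 and 6 months) to a feasibility RCT". The Quantitative Data analysis section then disposes of its analysis in one sentence, "Quantitative analyses are not required: recruitment and retention rates will be simple percentages", supported only by a reference to a thematic-analysis paper.

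Other sections ask more of the numbers:

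- **Evidence of feasibility** poses the question that the rates must answer: "Can sufficient numbers of families be recruited and retained such that a full-scale RCT is likely to be feasible".
- **Follow-up** says that the follow-up will indicate the retention a larger trial could expect.
- **Data Collection, Baseline** plans to look at missing data on the candidate measures, with about 30 families per measure, and at "mean scores and standard deviations (to support sample size calculations for a future definitive RCT").
- **Sampling** gives the size: "We intend to recruit a sample of 30 families in Phase 2, 15 families will be randomly allocated to each group". It declines a power calculation ("formal power calculations are not appropriate for this largely qualitative study") and says that information from this study and from others will feed into the sizing of a definitive trial.

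No interval or statement of precision appears anywhere in the protocol.

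**The concern.** Two things are wrong with the sentence as it stands.

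First, it conflicts with the Baseline section. Summarising missing data, means and standard deviations in order to size a later trial is a quantitative analysis. Anyone who writes an analysis plan from the analysis section alone would leave that work out.

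Second, the method it names does not match the use of the result. A percentage describes the 30 families in hand. The protocol wants to learn from them about a future, larger trial, and that step needs a statement of how far the observed rate may lie from the underlying one. At this sample size the distance is large enough to change the answer to the feasibility question. The same holds for the standard deviations, because required sample size grows with the square of the standard deviation.

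**Working it through.** **Inputs from the protocol.** 30 families, 15 per arm (Sampling); 1:1 allocation, "A central randomisation facility will randomise patients (1:1) to IPS or SAU" (Randomisation and allocation); about 30 families per measure (Baseline). The split is consistent: 15 + 15 = 30. There is no derivation of the 30 to reproduce, since no alpha, power, effect size or target precision is given.

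**Illustrative inputs (assumptions).** A retention count of 22 of 30 is used as an example. It is the whole number nearest to 0.72 × 30 = 21.6, 72% being the only retention rate in the document. The protocol gives no standard deviation for any measure, so those results are shown as multiples of the observed value.

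**Step 1: retention.** The exact (Clopper-Pearson) 95% limits for x of n are the 2.5% quantile of Beta(x, n − x + 1) and the 97.5% quantile of Beta(x + 1, n − x).

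| Retained | Rate | Exact 95% CI |
|---|---|---|
| 21/30 | 70% | 51% to 85% |
| 22/30 | 73% | 54% to 88% |
| 24/30 | 80% | 61% to 92% |
| 27/30 | 90% | 73% to 98% |
| 11/15 (one arm) | 73% | 45% to 92% |

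At 22/30 the interval is about 34 percentage points wide. The Wilson method gives a similar result, 56% to 86%.

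**Step 2: recruitment.** Its denominator is the number of families approached or eligible, which the protocol does not state; it is not 30. If 60 were approached and 30 joined (assumption), the rate would be 50% with an exact interval of 37% to 63%.

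**Step 3: standard deviation.** The 95% limits are the observed SD times √(df/χ²₀.₉₇₅) and √(df/χ²₀.₀₂₅). Required N is proportional to SD², so its multipliers are the squares.

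- 30 families, df = 29: √(29/45.72) = 0.80 and √(29/16.05) = 1.34; required N 0.63 to 1.81 times.
- 30 families pooled within arm, df = 28: 0.79 to 1.35; required N 0.63 to 1.83 times.
- 22 families at follow-up, df = 21: 0.77 to 1.43; required N 0.59 to 2.04 times.

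**Step 4: what this means for a later trial.** Assume 90% power, two-sided 5%, and a target difference of 0.4 observed SDs. Then n per arm = 2 × (1.960 + 1.282)² / 0.4² = 131.4, rounded up to 132. Across the df = 29 interval for the SD this becomes 84 to 238 per arm. If the true SD lay at the upper limit, 132 per arm would give about 68% power.

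**The case against.** The strongest reply is that the conflict is one of wording. The Baseline section says that the candidate measures are not there to measure trial outcomes and that only basic features of the data will be examined. Sampling says that no quantitative outcomes other than the rates are studied. Read together, the disputed sentence may mean only that no comparative testing is planned. Intervals and tables by arm are also details that a statistical analysis plan often supplies, and that document is not at hand.

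Part of this stands. The phrase about simple percentages does not forbid an interval or a breakdown by arm, and a reader should not infer that it does. Declining a power calculation is proper in a feasibility study. But the sentence is more than silence: it says that analysis is not required, while another section plans some.

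Three stronger readings are tempting and are not supported:

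- **That the standard deviations will be used as if exact.** If a trial were sized for 90% power on this SD alone, true power would fall below 80% with probability P(χ²/df < ((1.960 + 0.842)/(1.960 + 1.282))²), which is 17% at n = 30 and 21% at n = 22. The protocol does not say that it will do this. It speaks of supporting and informing the calculation, with other studies alongside.
- **That 72% is the plan's retention benchmark.** The statement "We have managed to retain 72% of these families over 2.5 years" reports the team's record in families whose children were entering foster care. It is not a target for six months in this population.
- **That both primary rates rest on 30 families.** Thirty is the denominator for retention only. For recruitment, the Outcomes table asks whether 30 eligible families can be identified and randomised.

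**Conclusion.** The point holds in this form: the analysis section contradicts the Baseline section, and simple percentages alone do not serve the feasibility question or the projection to a larger trial. The size of the problem is an interval of about 34 percentage points for retention near 73%, 45% to 92% within one arm at the same rate, and a 0.63 to 1.81 fold range in a sample size derived from an SD on 30 families.

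The retention figures assume full recruitment of 30 and an illustrative count of 22. The SD intervals assume roughly normal scores; the per-arm illustration adds assumed power, alpha and effect size. None of this shows that 30 families is too few for a feasibility study, or that a later trial will be mis-sized. It shows that the uncertainty is material and that the protocol neither states it nor says that it will be allowed for.

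**What to change.** Replace the sentence under Quantitative Data analysis with the descriptive analyses that the protocol already intends:

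- Recruitment as n/N with an exact 95% confidence interval, naming the denominator (families approached, or families eligible).
- Retention as n/N of families randomised, at 3 and 6 months as in the Summary, with exact 95% intervals, overall and by arm. The Follow-up section gives a single 3 to 6 month window, so the time points should be made to agree.
- Completeness, means and within-arm pooled standard deviations of each candidate measure, with 95% intervals, cross-referenced to the Baseline section.
- A statement that these standard deviations, together with other studies, will inform the definitive sample size with allowance for their uncertainty.

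Remove the thematic-analysis citation from this section. In Sampling, state the precision that 30 families give for retention, for example 51% to 85% if 21 are retained and 73% to 98% if 27 are.

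The earlier trial's 72% should not be turned into a pass mark, and no retention cut-off is proposed here.

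The cost is a short paragraph and a little analysis time. Procedures and participant burden are unchanged. The downside is that the published intervals will look wide.

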
Voices of Parent Collaborators won't be given equal weight.
	
Parent Collaborators will lead development sessions and this type of risk (including power dynamics and status quo) will be addressed from the beginning of the development sessions in Phase 1. It will also be written into the terms of reference. The research team will aim to reduce any power imbalances in these environments and support parent collaborators, including inviting a coproduction expert to address sharing of power within the coproduction team.

Timeline

Milestone Number	Dates	Activity	Staff responsible/leading
1	31/03/22	
Project set-up actions, pre-official project start date:
 
 Incorporated learning from parent-led Aberlour Trust-funded qualitative study Secured ethical and governance research approval from UoG, NSPCC and LAs Recruited research staff (delivery staff are already in place) Recruited parent collaborators Attend WWCSO facilitated kick-off meeting Trial protocol draft submitted to WWCSO for comment 	[name]
2	31/05/22	
 Host UoG/NSPCC stakeholder engagement workshop with CAMHS, AMHS and social care Completed 6-8 focus groups with practitioners/parents/stakeholders to inform point below Completed coproduction of IPS intervention, understanding of services as usual context, and research processes (including finalising research measures for a definitive RCT) 	[name]/[name]
3	31/12/22	
 We will produce an outline model of IPS and a Theory of Change, describing the various elements of assessment and intervention and the tools, measures and professional roles involved in IPS. This will be disseminated through the NSPCC website Draft Trial Protocol to be submitted in WWCSO template, including incorporation of WWCSO feedback 	[name]/[name]
4	31/01/23	
 Consolidate discussions with potential sites for a definitive RCT 	[name]/[name]

		
 Concluded preparation for Phase 2 (participant recruitment pathways and IPS delivery readiness) Shared bi-annual report with WWCS Final Trial protocol submitted to WWCS with all required comments and feedback incorporated, ready for publishing Protocol published on the Open Science Framework (OSF), Completed IPS team poverty awareness training 	


Appendices

1. Interview Participant Consent Form
2. Interview Participant Sheet
3. Initial Referral with Consent Form
4. Participant Consent Form
5. Participant Information Sheet
6. Participant Privacy Notice
7. Phase 1 Stakeholder Interview Topic Guide
8. Phase 2 Stakeholder Interview Topic Guide

Partnership for Change Trial

Phase 1 Topic Guides

Topic Guide Questions:**Focus Group/one to one professional interview questions:**

[send this question out in advance – request written responses?] With ‘at risk’ and ‘in need’ children in mind can you describe the legal and service landscape in your local area (SAU and specific provision)?

1. What are the differing pathways into services for families and who would usually be involved (and at which points)? (Prompt: can you think of other routes or examples?)
2. Do you feel that children are appropriately referred for assessments in terms of 1) safety and 2) need (for example: medical, neurodevelopmental, physical, over-all development, etc.)?
3. What facilitates parent and child journeys into and out of services?
4. What barriers are you aware of to parent and child journeys into and out of services? (Prompt) What professional and personal barriers are there to families progressing through support services are you aware of?
5. What sort of professional understanding/service developments do you now feel are necessary to support at risk families better? (Prompt: any thoughts around intersectional issues, safeguarding, trauma-informed and poverty-aware approaches?) (Any thoughts around training needs and requirements for people engaging with families ‘at risk’?)
6. In future service developments what are your thoughts around working alongside workers with lived experience?

One to one parent interview questions:

(n=6-8 across 2 sites): 8 would be preferred number minimum if one to one interviews are the preferred method)

1. Can you tell us about your journey into services as a parent?
2. What is your families experience of services since then?
3. What if anything, has been helpful to your family?
4. What if anything, has been less helpful?
5. Do you feel your needs have been met? (If yes, how? If no, why not?)
6. What if anything would you like to see change?
7. What sort of service developments would improve parent and child journeys?

Parent collaborator FG questions:

1. What motivated you to become involved in the Partnership for Change Study?
2. Overall, how have you found the experience of being a parent collaborator? (prompt: perceptions of role)
3. How has the process of developing the CAPS Programme worked in practice? (Should identify pros and cons)
4. For you, what ways of working have been helpful in terms of coproducing CAPS with other stakeholder groups?
5. Is there anything about that process that you would improve, and if so how?

Parent Collaborator Parent-Reported Measures Development Focus Group

1. What was the most important or significant issue, that you wish services paid more attention to when your family was involved with social work? (*What was really important to you at that time?*)
2. What were the most important changes you would have liked to have seen in your lives at that time?
3. Is there anything that you can think of that the Infant and Parent Support team could do to offer more support to families going through similar experiences?
4. From the first few questions, is anything that you think could help the research team capture this type of information? What would this have looked like?
5. How could we collect data on these? (Use stimulus material to prompt, for example illustrations of Likert scales)
6. How did you feel when you were receiving support from services previously?
 - a. How were you treated? How did you feel?
 - b. Was there anything in particular that was helpful or not helpful? (Prompts: Respect, stigma, ashamed, helpful, equality, level playing field, supported).
7. Thinking about how your family experienced accessing social work, mental health services, and/or other supports, what are ways that this experience could be improved in IPS?
8. What information could we collect to measure this?
9. Just before the break, we discussed how we can measure and collect data on outcomes. Now we would like to know how you think we should measure experience?
10. Is there anything that you would like to add?

Partnership for Change Phase 2 Topic Guides

First of all, can you tell me how your referral into services came about?

1. Can you tell me about your journey through the referral process?
2. Can you tell me how you felt about the possibility of being referred and accepted into either services included in the study?

Now, thinking now about the research part of your involvement in the Pfc Study:

3. How do you feel about how your involvement in the research has been explained to you (time commitment, questionnaire completion, interviews, methods used, RCT group allocation)? How did what was actually involved compare with your expectations?
4. Supplementary probing question if necessary: what do you understand about your involvement in the research?
5. How did you feel about the consent you gave and the points you agreed to? Did the information provided make sense to you? (Readability, accessing wider records, sharing information, researcher interviews, etc.)
6. How did you feel about the assessments used? (probe – potential burden, e.g. length of time it took and whether they liked the assessment method etc)
7. How did you feel about where and how assessments were completed? (venue, setting, comfort levels, engaging with staff, etc.)
8. How did you feel about the types of questions included in the questionnaires used as part of the assessment? Was there anything in particular that you would like to comment on? (relating to personal questions without leading participants)
9. Are there any questions not included that would have been helpful to cover that would help us understand your situation better? (Relating to income (money coming in and out of your family), access to travel to get places, access to services, cultural needs, etc.)
10. Are there any practical issues for you that the research team should be aware of? (travel, language, support, childcare?)
11. Up to now have there been any particular ways that you have been contacted that you have found particularly helpful/unhelpful? (Probes: text/phone/time of day/etc.)
12. Any other comments?

Professional Key Stakeholder Interviews for Phase 2

Feasibility of Methods

1. Can you tell us your thoughts on referral routes into the trial and into the new intervention if randomised that way?
2. If randomised to SAU, how did it work identifying and providing support for the family (if applicable)? (Prompt: enquire about each type of service if families received more than one)
3. What was your knowledge of the new intervention? Knew anything about/ had any links/ what they thought about the new intervention's content and delivery, duration etc. (Probe specifically for different aspects of intervention)
4. How did it fit with other services being delivered to families – eg overlap, filling a gap, replacing/ negating the need for other services (if so which)
5. Referrals into other services from and around the new intervention – can they tell us anything about that worked from their perspective.
6. What went well/ is good about the new intervention?
7. Do you have any suggestions for improvements to the research and to the intervention?

Parent Collaborator FG questions:

Explores RQ1, RQ3 & RQ5

6. What motivated you to become involved in the Partnership for Change Study?
7. How would you describe your role as a Parent Collaborator?
8. Overall, how have you found the experience of being a Parent Collaborator?
9. How has the process of developing the intervention worked in practice? (Should identify pros and cons)
10. For you, what ways of working have been helpful in terms of coproducing the new intervention with other stakeholder groups?
11. What has been less helpful?
12. What are the challenges, or potential challenges with the new intervention?
13. Is there anything about that process that you would improve, and if so how?
